## Dosing Schedule A-2: AlloStim® without cryoablation

The priming step: Subjects will receive an ID injection of AlloStim® (1 ml) on Days 0, 3, 7, 10 and 14.

The vaccination step: Subjects will receive an IV injection of AlloStim® (3 ml) of on Day 21. The activation step: Subjects will receive an IV infusion of AlloStim® (3ml) on Day 28. The booster step: Subjects will receive three (optional) IV booster infusions of AlloStim® (3ml), one on Day 49, a second on Day 77.

Two types of toxicity are assessed for determination of whether a Dose Limiting Toxicity (DLT) has occurred. An acute dose limiting toxicity (ADLT) is assessed within 48h of a dose administration during the priming, vaccination and activation steps of each protocol. Cumulative dose limiting toxicity (CDLT) is assessed during the complete Safety Evaluation Period including any ADLT that occurs in the booster dosing.

An ADLT is defined as the occurrence of any of the following within 48h of dosing:

- Any  $\geq$  Grade 3 local injection site reaction;
- Any  $\geq$  Grade 3 infusion related symptoms of duration > 2 days;
- Any  $\geq$  Grade 4 infusion reaction of any duration

For any Grade 1-2 acute toxicity, the study drug administration schedule can continue to the next scheduled dose. If an ADLT is observed, the subject will be followed until the toxicity is resolved or the subject is stable. No further dosing for that subject will occur after an ADLT event.

A CDLT event is defined as the occurrence of any of the following within the Safety Evaluation Period:

- Any  $\geq$  Grade 3 graft vs. host disease
- Any toxicity  $\geq$  Grade 3 that is probably or definitely related to the study drug;
- Any toxicity not present at baseline that occurs at  $\geq$  Grade 4
- Any autoimmune toxicity  $\geq$  Grade 3 not present at baseline

All adverse events (AEs) and serious adverse events (SAEs), regardless of attribution to the study drug, will be coded, graded and become part of the final safety report for each cohort. The Data Safety Monitoring Board (DSMB) will review the safety data on each cohort and recommend whether to advance enrollment to the next cohort.

The development of any Grade 4 or greater toxicity in any subject at any time will prompt a review of safety data by the Sponsor, PI and the DSMB prior to accrual of any additional subjects. It is recognized that Grade 4 events and death can occur in this population due to disease progression. Therefore, dosing will continue for currently enrolled subjects at the occurrence of a grade 4 event according to protocol unless the PI determines the Grade 4 or greater event is definitely or probably related to the study drug. If attribution is assigned to the study drug dosing will be suspended pending review by the DSMB.

In accordance with the 3+3 design, three subjects will be accrued into the first dosing schedule. If during the priming, vaccination and activation steps no ADLT are observed in any of the three subjects, accrual into the next cohort is allowed. If an ADLT occurs in two of the three subjects, no further dose frequency escalation is allowed. If ADLT occurs in one of

the three subjects, three additional subjects will be accrued into the same cohort. If no ADLT occurs within the additional three subjects, accrual into the next cohort can begin. If an ADLT is observed in any of the additional three subjects, no further dose escalation is permitted.

The development of any DLT toxicity in  $\geq$  33% of the accumulated number of subjects in any and all dosing schedules during the Safety Evaluation Period will result in protocol discontinuation.

At the completion of the Safety Evaluation Period for all cohorts, the safety evaluation of Part 1 will be considered completed and all enrollment will be closed. Efficacy evaluation will continue monthly for each subject until death or loss to follow-up.

## **Objectives:**

## **Primary Objectives**

1. To evaluate the safety and anti-tumor effect of AlloStim® with or without cryoablation

## **Exploratory Objectives**

- 1. To assess the longitudinal changes in tumor burden by RECIST and compare these changes with the histopathological analysis of corresponding biopsies.
- 2. To assess whether immune response correlates with RECIST or histopathology and Overall Survival (OS).

## **Study Population:**

Adult patients  $\geq 18$  years and  $\leq 80$  years with adequate performance status (ECOG <2) and adequate organ function with metastatic, histologically confirmed adenocarcinoma of the rectum or colon presenting with metastatic disease and has been previously treated with two lines of active chemotherapy with or without bevacizumab and also present with a liver tumor lesion safely accessible for percutaneous cryoablation.

## **Total Number of Subjects:**

Part 1 will accrue 3 subjects in A-1 and 3 subjects in A-2 and continue with an additional up to 25 subjects in the favored protocol.

#### **Study Duration:**

Part 1 is projected to last 30 to 72 weeks. It is projected that approximately one subject will be accrued every two weeks. Part 2 is projected to last an additional 72-104 weeks Subjects, as long as they are available for follow-up, will be followed monthly for 12 months following last dose administration for survival and quarterly thereafter.

#### **Inclusion Criteria:**

Each subject must meet the following criteria to be enrolled in this study:

- 1. Adult males and female subjects aged 18-80 years at screening visit
- 2. Pathologically confirmed diagnosis of colorectal adenocarcinoma
- 3. Presenting with metastatic disease:
  - Primary can be intact or previously resected
  - Metastatic lesion(s) in liver must be non-resectable
  - Extrahepatic disease acceptable
- 4. At least one liver lesion able to be visualized by ultrasound and determined to be

safely assessable for percutaneous cryoablation (if schedule includes cryoablation)

- 5. Previous treatment failure of two previous lines of active systemic chemotherapy:
  - Previous chemotherapy must have included an oxaliplatin-containing (e.g. FOLFOX) and an irinotecan-containing (e.g. FOLFIRI) regimen
    - With or without bevacizumab
    - o Administered in adjuvant setting or for treatment of metastatic disease
    - o If KRAS wild type, must have at least one prior anti-EGFR therapy
    - Treatment failure can be due to disease progression or toxicity
    - Disease progression on second line therapy must be documented radiologically and must have occurred during or within 30 days following the last administration of treatment for metastatic disease
- 6. ECOG performance score: 0-1
- 7. Adequate hematological function:
  - Absolute granulocyte count  $\geq 1,200/\text{mm}^3$
  - Platelet count  $\geq 100,000/\text{mm}^3$
  - $\circ$  PT/INR  $\leq$  1.5 or correctable to <1.5 at time of interventional procedures
  - Hemoglobin  $\ge 9 \text{ g/dL}$  (may be corrected by transfusion)
- 8. Adequate Organ Function:
  - $\circ$  Creatinine  $\leq 1.5 \text{ mg/dL}$
  - Total bilirubin  $\leq 1.5$  times upper limit of normal (ULN)
  - Alkaline phosphatase  $\leq 2.5$  times ULN \*
  - Aspartate aminotransferase (AST) or (SGOT)  $\leq$  2.5 times ULN \*
  - Alanine aminotransferase (ALT) or (SGPT)  $\leq$  2.5 times ULN\*
    - \*≤ 5 ULN if liver involvement)
- 9. EKG without clinically relevant abnormalities
- 10. Female subjects: Not pregnant or lactating
- 11. Patients with child bearing potential must agree to use adequate contraception
- 12. Study specific informed consent in the native language of the subject.

## **Exclusion Criteria:**

Subjects with any of the following will be excluded from the participation in the study:

- 1. Bowel obstruction or high risk for obstruction
- 2. Moderate or severe ascites requiring medical intervention
- 3. Clinical evidence or radiological evidence of brain metastasis or leptomeningeal involvement
- 4. Symptomatic asthma or COPD
- Pulmonary lymphangitis or symptomatic pleural effusion (grade ≥ 2) that results in pulmonary dysfunction requiring active treatment or oxygen saturation <92% on room air
- 6. Bevacizumab (Avastin®) treatment within 6 weeks of scheduled cryoablation procedure (if schedule includes cryoablation)
- 7. Regorafenib prior to the Study Period
- 8. Previous treatment with TAS102
- 9. Any of the following mood disorders: active major depressive episode, history of

suicidal attempt or ideation

- 10. Taking anticoagulant medication for concomitant medical condition (unless can be safely discontinued for invasive cryoablation, biopsy and intratumoral injection procedures)
- 11. Prior allogeneic bone marrow/stem cell or solid organ transplant
- 12. Chronic use (> 2 weeks) of greater than physiologic doses of a corticosteroid agent (dose equivalent to > 5 mg/day of prednisone) within 30 days of the first day of study drug treatment
  - Topical corticosteroids are permitted
- 13. Prior diagnosis of an active autoimmune disease (e.g., rheumatoid arthritis, multiple sclerosis, autoimmune thyroid disease, uveitis). Well controlled Type I diabetes allowed
- 14. Prior experimental therapy
- 15. History of blood transfusion reactions
- 16. Known allergy to bovine products
- 17. Progressive viral or bacterial infection
  - All infections must be resolved and the subject must remain afebrile for seven days without antibiotics prior to being placed on study
- 18. Cardiac disease of symptomatic nature
- 19. History of HIV positivity or AIDS
- 20. Concurrent medication known to interfere with platelet function or coagulation (e.g., aspirin, ibuprofen, clopidogrel, or warfarin) unless such medications can be discontinued for an appropriate time period based on the drug half-life and known activity (e.g., aspirin for 7 days) prior to cryoablation and biopsy procedures
- 21. History of severe hypersensitivity to monoclonal antibody drugs or any contraindication to any of the study drugs
- 22. Psychiatric or addictive disorders or other condition that, in the opinion of the investigator, would preclude study participation.
- 23. Subjects that lack ability to provide consent for themselves.

#### **Endpoints:**

#### Primary endpoint: Safety

**Exploratory Endpoints:** Correlation of immune response with tumor burden by RECIST, histopathology and OS.

#### Safety Assessments:

The following evaluations will be used to assess the safety of the investigational product:

- Physical examination, vital signs and laboratory evaluations (including a CBC with differential and comprehensive metabolic panel (CMP), coagulation factors, C-reactive protein (CRP), total IgG and IgM, erythrocyte sedimentation rate, serum lipase, and autoimmune blood screens).
- Adverse Events (AEs) recording according to the National Cancer Institute (NCI) Terminology Criteria for Adverse Events (CTCAE) version 4.03.
- Interrogation of subject, caregivers and family regarding any changes in health condition, in person or by telephone.

#### **Radiology Assessment:**

All subjects will undergo a CT scan of the head, chest, abdomen and pelvis with and without contrast (contrast can be withheld if medically indicated) at baseline and at Day 91 at same time as biopsy.

As it is difficult to determine if subjects are responding or progressing after immunotherapy by standard radiological methods and RECIST criteria, the analysis of the CT scans is conducted as an experimental end-point. It is known that after immunotherapy that subjects can develop new lesions, experience lymphadenopathy and interval size increases in tumors. These changes would normally be documented as progression. However, in immunotherapy, the changes could represent "pseudo-progression". In some cases, the changes could indicate actual progression, but a response can still occur months after immunotherapy. Other times, immunotherapy can cause a stable disease condition that results in increased survival.

The changes in the images will be analyzed by RECIST and other accepted and novel experimental methods in order to retrospectively determine a method that best correlates with survival outcomes. The CT scans are scheduled on the same day as biopsy procedures in order to correlate the radiological images with pathological response. It is believed that patterns of necrosis, fibrosis and immune cell infiltration patterns with HU numbers on the radiographic images may provide correlates that could distinguish immune response from progression or be predictive of a survival response. Radiographic images can be reviewed by the site radiologists according to established methods. At the discretion of the PI, select subjects may be further evaluated by MRI or PET in order to attempt to distinguish between radiological "pseudo-progression" due to an immune response and actual progression.

## Histopathology Assessment:

Subjects will undergo mandatory tumor biopsies of a target lesion at baseline, during intratumoral injections (Schedule A-1) and at Day 91. The intratumoral procedures use a trocar that will have already been inserted into the tumor to conduct the intratumoral injection and thus these biopsies will not add an additional interventional procedure on day 21 Schedule A-1

Additional biopsies will be conducted only if subjects separately consent. Failure to consent for the additional biopsy procedures will not disqualify subjects.

The harvested tissue will be prepared in paraffin blocks and read centrally by a pathologist appointed by the Sponsor. The amount of tumor burden estimated from the pathological evaluation will be compared with the amount of burden shown on the CT images. The amount and type of immune cell infiltration (immunohistochemical analysis), existence of coagulative necrosis, necrotic tumor and fibrosis will also be documented and correlated to the radiological images.

## **Immunological Monitoring Assessments:**

Research blood draws for monitoring of immunological response will be drawn at day 0 prior to study drug injection (baseline). A research blood draw is scheduled prior to study drug administration on Day 0, Day 28, Day 56 and Day 84 in Schedule A-1 and Day 0,21, 49 and 77 in Schedule A-2.

Immunological tests include: engraftment study (HLA), serum cytokines and polyclonal

Th1/Th2 balance. Seroconversion to IL-12 positivity will be evaluated as a possible biomarker that can predict response and extended survival. Development of a biomarker is important, as standard measures such as RECIST and tumor markers don't necessarily correlate with immune response mechanisms.

The Sponsor will prepare and label blood collection tubes for each research blood draw day. The collected research blood will be processed per Sponsor's SOP at or near the site in a laboratory approved by the Sponsor. The laboratory will isolate and store PBMC, serum and plasma for subsequent immunological testing. These samples will be transported in bulk using a dry shipper to the Sponsor's laboratory in Jerusalem for analysis. The research blood collection days are designed to obtain information on the mechanism of action of the drug. It is important that the minimum required amount of blood is collected and processed in accordance with the SOPs. The PI should consider placement of port or indwelling catheter in order to facilitate these blood draws.

## **Clinical Laboratory Tests:**

Changes in laboratory levels are evaluated in order to determine if the study drug is related to, or might cause, any changes in serum chemistry, hematological function, liver or kidney function, or maintenance of immune self-tolerance (autoimmune tests). All subjects will be monitored for changes in laboratory values in CBC, CMP (including liver function test, kidney function tests) lipase, total IgG and IgM, erythrocyte sedimentation rate, and CRP at baseline and weekly during the Safety Evaluation Period. Coagulation studies (PT, PTT, and INR) are conducted at baseline and prior to interventional procedures (biopsy, cryoablation and intratumoral injections). An autoimmune panel will be assessed on day 0 (baseline, prior to drug administration) and on the last day of the Safety Evaluation Period.

The laboratory reports should be de-identified and provided to the Sponsor. The Sponsor will provide graphs indicating the changing values of select markers. The graphs will be provided to the PI or designee for review and indication of clinical significant findings.

## **Statistical Analysis:**

Safety analyses will be performed on the safety population, defined as all subjects in the Intent to Treat (ITT) population that received any dose of study medication. The number of AEs reported will be summarized. Subjects will be censored is still alive at data cut-off or if they withdraw consent. The incidence and percentage of subjects with at least one occurrence of a preferred term will be included, according to the most severe NCI-CTCAE Version 4.03 grade.

Causality (relationship to study drug) will be summarized separately. Duration of AE will be determined and included in the listings along with action taken and outcome.

Laboratory results will be classified according to NCI-CTCAE Version 4.03. Incidence of laboratory abnormalities will be summarized; laboratory results not corresponding to an NCI-CTCAE Version 4.03 terms will not be graded. Laboratory toxicity shifts from baseline to worst grade will also be provided.

Any clinically significant results from physical examination and vital signs measurements will be tabulated.

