Therefore, the mechanisms of autoimmune disease serve as a model for developing strategies to break immune tolerance to tumors. A key mechanism for breaking self-tolerance and induction of autoimmunity is related to inflammation. Autoimmune attack of self-tissues requires two conditions: activated T-cells and the "conditioning" of the target organ by irradiation or infection [62]. These two conditions are created in the CryoVaxTM protocol by first an ablation of a tumor lesion and then intratumoral injection of allogeneic activated immune cells. The combination creates an inflammatory microenvironment around the dead tumor cells.

In order to develop an effective immunotherapy strategy for metastatic cancer, new approaches are required that not only can create and enhance tumor-specific immunity, but also are able to counter-act the ability of the tumor to evade immune destruction. The experimental drug, AlloStim®, is designed to break tolerance to tumor tissues by taking advantage of the known mechanisms of breaking tolerance to self-tissue in autoimmune disease. AlloStim® provides a highly inflammatory environment. Inflammation in the presence of tumor tissue that has died pathologically is a formula that has potential to break tolerance.

Type 1 cytokines including IL-1, TNF $\alpha$ , IFN- $\gamma$ , IL-12, IL-18, and GM-CSF are generally believed to be required components of therapeutic cancer vaccines. AlloStim® cells are differentiated in culture to produce large amounts of these Type 1 cytokines. Because AlloStim® cells are allogeneic and recognized as foreign by the host immune system, they will be rejected by the host. Since these foreign cells produce large amounts of Type 1 cytokines, they are expected to steer the immune response to the foreign antigens to Th1. In this manner, the rejection process is expected to increase the number of Th1 memory immune cells in the circulation of patients injected with AlloStim®. This is significant because cancer patients are known to have an excess of Th2 immune cells and absence of Th1 cells. This imbalance is thought to be a mechanism of tumor immune evasion.

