# 9. STUDY ENDPOINTS

# 9.1.PRIMARY ENDPOINT

Safety will be the primary endpoint of this study and will be evaluated on the basis of the following parameters:

- Physical examination and vital signs (temperature, blood pressure, pulse rate, respiratory rate, and blood oxygen saturation).
- Clinical laboratory profile (complete blood count (CBC), comprehensive metabolic panel (CMP), C-reactive protein (CRP), coagulation factors and autoimmune parameters.
- Adverse events according to the National Cancer Institute (NCI) Terminology Criteria for Adverse Events (CTCAE) version 4.03 (refer to section 15 for AE/SAE management and reporting):

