#### **15. ADVERSE EVENTS**

An adverse event (AE) is any untoward medical occurrence in a trial subject that has been administered the study drug; the event does not necessarily have to have a causal relationship with AlloStim® treatment or usage.

All observed or volunteered AEs, regardless of causal relationship to the investigational product, will be recorded as an adverse event on a supplied case report form (CRF) or electronic CRF (eCRF). Events involving adverse drug reactions, illnesses with onset during the study, or exacerbations of preexisting illnesses should also be recorded as AEs.

Exacerbation of pre-existing illness, including the disease under study, is defined as manifestation (sign or symptom) of the illness that indicates a significant increase in the severity of the illness as compared to the severity noted at the start of the trial and the known normal course of disease progression for stage IV colorectal cancer. This may include worsening or increase in severity of signs or symptoms of the illness, increase in frequency of signs and symptoms of an intermittent illness, or the appearance of new manifestations/complications. Exacerbation of a pre-existing illness should be considered when a subject requires new or additional concomitant drug or non-drug therapy for the treatment of that illness during the trial.

Lack of, or insufficient clinical response, benefit, efficacy or therapeutic effect, should not be recorded as an AE. The investigator must make the distinction between exacerbation of preexisting illness and lack of therapeutic efficacy. The investigator can take into consideration the results of radiology and pathology exams and immunological monitoring data when making this assessment.

In addition, abnormal objective diagnostic procedures findings (e.g., abnormal laboratory test results) should be recorded as an AE if it is fulfills one or more of the following:

- Results in subject's withdrawal by the Investigator;
- Is associated with an SAE;
- Is associated with clinical signs or symptoms;
- Is considered by the physician to be of clinical significance;
- Requires the subject to have study therapy discontinued, modified, or interrupted;
- Requires the subject to receive specific corrective therapy; and
- Requires diagnostic evaluation to assess the risk to the subject.

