#### Table 9 NCI-CTCAE v 4.03 Infusion-related Allergic or Autoimmune Toxicity

Protocol Date: December 23, 2014 Amendment Date: September 12, 2017 Page 69 of 94

| Adverse
Event                | Grade 1   | Grade 2   | Grade 3   | Grade 4   | Grade 5 |
|---------------------------------|---|---|---|---|---------|
| mune
disorder                | serologic or
other evidence
of autoimmune
reaction, with
normal organ
function;
intervention not
indicated | autoimmune
reaction involving a
nonessential
organ or function
(e.g., hypothyroidism)   | involving major organ
(e.g., colitis, anemia,
myocarditis, kidney)  | threatening
consequences;
urgent
intervention
indicated                       |         |
| Cytokine
release
syndrome | Mild reaction;
infusion
interruption
not
indicated;
intervention
not
indicated                             | Therapy or infusion
interruption indicated
but
responds promptly to
symptomatic
treatment
(e.g., antihistamines,
NSAIDS, narcotics,
I.V.
fluids); prophylactic
medications indicated
for $\leq 24$ hrs | Prolonged (e.g., not
rapidly responsive to
symptomatic
medication
and/or brief
interruption
of infusion); recurrence
of symptoms following
initial improvement;
hospitalization
indicated
for clinical sequelae
(e.g.,
renal impairment,
pulmonary infiltrates) | Life-
threatening
consequences;
pressor or
ventilator
support
indicated | Death   |

The following are treatment guidelines for AlloStim® infusion reactions:

#### Grade 1

- Monitor the subject for worsening of condition.
- For subsequent infusions or IV push, premedicate with 25-50mg diphenhydramine PO/IV, 150mg ranitidine (Zantac) PO or other H-2 blocker, 25-50mg PO indomethacin (or equivalent NSAID). During or after the infusion if showed signs of infusion reactions in prior intravenous dosing (rash, itching, shortness of breath) at the investigator's discretion.

# Grade 2

- Monitor for worsening of condition.
- Administer diphenhydramine hydrochloride 50 mg IV (or equivalent), acetaminophen 650 mg orally for fever, and oxygen.

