#### 16.1.4. Adverse Events

All reported terms (investigator descriptions) for AEs will be coded using the Medical Dictionary for Regulatory Activities (MedDRA). The incidence of AEs will be summarized for those events that occur on or after the date of the first treatment (TEAE: Treatment-Emergent Adverse Events). All SAEs and TEAEs leading to withdrawal, and or other significant TEAEs will be listed separately. The data will be summarized as follow:

- all TEAEs,
- TEAEs related to Study drug,
- Serious TEAEs,
- Serious TEAEs related to Study drug,
- TEAEs resulting in death,
- TEAEs leading to withdrawal.

The incidence of TEAEs will be summarized by system organ classification and preferred term by severity and relationship to study medication. All AEs will be included in the data listings.

Laboratory results will be classified according to NCI-CTCAE Version 4.03. Incidence of laboratory abnormalities will be summarized; laboratory results not corresponding to an NCI-CTCAE Version 4.03 term will not be graded. Laboratory toxicity shifts from baseline to worst grade will also be provided.

The results from medical history, physical examination, and vital signs measurements will be tabulated.

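### The plan does not say how autoantibody results are graded or compared with Day 0, so new autoimmune-panel positives may be missed or under-reported in the primary safety results

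*Combined protocol and SAP*

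**What the plan says.** Section 9.1 names "coagulation factors and autoimmune parameters" within the laboratory profile that makes up the primary safety endpoint. Under Clinical Laboratory Tests, the abstract explains that laboratory changes are assessed to see whether the drug affects, among other things, immune self-tolerance. It places the autoimmune panel on Day 0 and on the last day of the Safety Evaluation Period. Section 11.2.3 lists the panel: complement C3, anti-DNA, ANA, AMA, SMA and LKM. Section 6.3 shows why this matters for this product, which is "designed to break tolerance to tumor tissues by taking advantage of the known mechanisms of breaking tolerance to self-tissue in autoimmune disease".

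For analysis, the abstract and Section 16.1.4 classify laboratory results by CTCAE v4.03, promise a summary of the incidence of abnormalities, and leave results without a CTCAE term ungraded ("laboratory results not corresponding to an NCI-CTCAE Version 4.03 terms will not be graded"). Section 16.1.4 adds: "Laboratory toxicity shifts from baseline to worst grade will also be provided". Section 16.1 describes the incidence summary more narrowly, as covering clinically significant laboratory abnormalities.

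Section 15 makes an abnormal test an adverse event if it meets any one of seven criteria. One of them is "Is considered by the physician to be of clinical significance". Table 9, in Section 15.4, gives as Grade 1 autoimmune disorder an asymptomatic state with "serologic or other evidence of autoimmune reaction, with normal organ function" and no intervention indicated.

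**The concern.** Whether self-tolerance is maintained is a question about change within a subject: negative before treatment, positive after. A grade shift answers it only if the result carries a grade. ANA, AMA, SMA, LKM and anti-DNA are usually reported as negative, positive or a titre, and the plan does not say which grade, if any, they receive. An incidence count does not answer it either, because a subject already positive on Day 0 and a converter are counted alike.

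At stake is the laboratory safety signal most specific to a product intended to break tolerance. It also has some bearing on choosing a schedule, since Section 7.1 makes fewest adverse events one of the grounds for that choice. With three subjects per schedule in Part 1, one or two events recorded or not recorded at discretion could change how the two schedules compare.

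**Working it through.** The plan gives no figure for this point, so the check is mainly a comparison of passages.

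**1. Can a conversion enter the shift table?** Only if panel results map to a CTCAE term. Table 9 offers one (autoimmune disorder, Grade 1). Sections 16.1.4 and 15.1.1 do not refer to it, and the statistical text in the abstract does not either. If the panel is mapped, a Grade 0 to 1 shift is possible. If it is not, the rule on ungraded results applies and no shift is shown. The documents allow both readings.

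**2. Does the incidence summary show it?** Section 16.1.4 sets no limit to graded tests, while Section 16.1 limits the summary to clinically significant abnormalities. Neither conditions on Day 0 status.

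**3. Does the adverse-event route show it?** Take a conversion that fits Table 9 Grade 1: no symptoms, normal organ function, no intervention. Against the seven criteria in Section 15:
- withdrawal by the investigator: ordinarily not met
- association with an SAE: ordinarily not met
- association with signs or symptoms: not met, since it is asymptomatic
- change or interruption of study therapy: ordinarily not met
- specific corrective therapy: not met, since no intervention is indicated
- clinical significance: a matter of judgment
- need for diagnostic evaluation: a matter of judgment

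So 7 - 5 = 2 criteria remain, and both are discretionary.

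**4. Are the data there to build a table?** The Safety Evaluation Period ends 28 days after the last dose. If both boosters are given:
- A-1: Day 84 + 28 = Day 112. Table 1 marks the panel on Days 0 and 91, and 112 - 91 = 21 days early. The ±3-day laboratory window in Section 12.1 does not cover that gap.
- A-2: Day 77 + 28 = Day 105. Table 2 marks the panel on Day 0 only.

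Read literally, Table 2 gives A-2 no post-baseline panel. The panel rows carry a footnote mark whose text is not in the document as read, so a footnote might qualify this.

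On capture, Section 15.1.1 puts every laboratory value on the CRF. Table 10 puts only the date and clinically significant autoimmune results there.

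**5. Illustrative size.** Inputs: n = 3 + 25 = 28, the most subjects on one schedule if Part 1 needs no expansion and Part 2 fills; an assumed conversion rate of 5% to 20%, which has no source in the documents.
- Expected conversions: 0.05 × 28 = 1.4; 0.20 × 28 = 5.6, or about 1 to 6 subjects.
- Exact (Clopper-Pearson) 95% limits for x of n: lower = Beta(0.025; x, n - x + 1), upper = Beta(0.975; x + 1, n - x). For x = 0 the upper limit is 1 - 0.025^(1/n) = 1 - 0.025^(1/28) = 0.123.

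| Reported | Estimate | Exact 95% CI |
|---|---|---|
| 0/28 | 0% | 0% to 12.3% |
| 1/28 | 3.6% | 0.1% to 18.3% |
| 5/28 | 17.9% | 6.1% to 36.9% |
| 6/28 | 21.4% | 8.3% to 41.0% |

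If five subjects convert, the same laboratory data could be reported as any count from 0 to 5, depending on the mapping and on investigators' judgments.

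**The case against.** The strongest reply is that ungraded does not mean unreported. The clause on grading sits beside a promise to summarize the incidence of abnormalities, which Section 16.1.4 does not restrict. Section 9.1 names autoimmune parameters in the primary endpoint. That is correct. A reader might infer that autoantibodies drop out of the safety results altogether; the documents do not support that. What remains is that an incidence count does not isolate converters and that Section 16.1 narrows the count.

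Second, the grading exclusion covers only results with no CTCAE term, and Table 9 supplies a term that could fit. This also stands: the defect is an unstated mapping, not an exclusion.

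Third, Section 15.4 introduces Table 9 for symptoms during or after infusion, so an asymptomatic conversion on an end-of-period panel is not plainly within its setting. It would be too firm to say that Section 15.4 makes every conversion a graded event. But the Grade 1 entry is itself asymptomatic, and CTCAE v4.03 grades all adverse events in this trial, so the tension with Section 15 is real.

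Fourth, it would be wrong to say that an abnormal test becomes an adverse event only if judged significant, since there are seven alternative criteria. Section 15.1.2 also asks investigators to be vigilant for immune-related events. For an asymptomatic conversion, however, the two routes left both depend on judgment.

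**Conclusion.** The point holds as an unspecified analysis. The plan names autoimmune parameters in its primary endpoint and states a before/after purpose for the panel, but it plans no analysis that shows conversion and does not say whether panel results can be graded. New autoantibodies may be missed or under-reported.

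The size cannot be fixed from the documents. The 0/28 versus 5/28 contrast is an illustration at the maximum sample size under an assumed rate. It does not predict that the trial would report zero, which would require that no conversion meets any adverse-event criterion and that none is mapped to Table 9.

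The consequence is limited. The autoimmune DLT criterion starts at Grade 3 (Section 8), so Grade 1 serology triggers no DLT rule. Choice of schedule also weighs efficacy and does not rest on this alone. The change is worth making because it is cheap and the endpoint is primary.

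**What to change.** In Section 16.1.4 and the abstract:
- For ANA, AMA, SMA, LKM and anti-DNA, add a table of Day 0 negative/positive by post-baseline negative/positive, by schedule. Use the local laboratory's cut-off and include every result, whatever its judged clinical significance. Report new conversions over subjects negative on Day 0 who have a post-baseline result, with an exact 95% CI.
- For C3, which is a level, and for other tests without a CTCAE grade, add a low/normal/high shift against the local range.
- State whether panel results map to the Table 9 autoimmune disorder term, and reconcile the adverse-event criteria in Section 15 with that entry. How a new positive should be recorded is for the sponsor and investigators to settle; the two passages need to agree.

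So that the table can be computed, also reconcile:
- the abstract's end-of-period panel with Table 1 (Day 91) and Table 2 (Day 0 only);
- Section 15.1.1 (all values on the CRF) with Table 10 (date and clinically significant autoimmune results only);
- the incidence wording in Section 16.1 with that in Section 16.1.4.

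The cost is one extra table and a few sentences. No sampling is needed beyond the panel that the abstract already requires, although a site working from Table 2 would be adding a draw in A-2.
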